DilaCheck® Trial

TITLE:

**Inter-examiner Agreement of a Novel Device for the Measurement of Cervical
Dilation in Labor: A Randomized Controlled Trial**

NCT Number: 03440723

Date of the Document: January 1, 2019

PROTOCOL

TITLE: Inter-examiner Agreement of a Novel Device for the Measurement of Cervical Dilatation in Labor: A Randomized Controlled Trial

ABBREVIATED TITLE: DilaCheck® Trial

PROTOCOL SUMMARY

Measurement of cervical dilation during late pregnancy and labor informs decisions in the management of labor and delivery. Prior published research suggests that practitioners are only 48 to 56% accurate when judging cervical simulators.¹⁻³ When measuring laboring women, two practitioners' measurements agree only 49% of the time.⁴ [name] of Elm Tree Medical Inc. (the Sponsor) developed a novel device, DilaCheck®, to enable practitioners to increase accuracy in cervical dilation measurements.

Elm Tree Medical completed a preliminary trial using a simulator similar to those used in prior studies. Fifty Labor and Delivery practitioners completed examinations using standard methods and then the device. Standard methods yielded an accuracy of 46%. With the device, accuracy increased to 96%, representing an 108% increase. The device was equally accurate regardless of years of experience or level of training. Standard methods resulted in a 10.5% rate of errors of two or greater centimeters from the true value. The device eliminated readings that were incorrect by more than one centimeter.

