The proposed study tests the novel DilaCheck® device *in vivo*. The target population is women presenting to the hospital for evaluation of labor or admitted to the Labor and Delivery unit for management of the first stage of labor. The Sponsor (Elm Tree Medical Inc.) trains providers working on the Labor and Delivery unit in the use of DilaCheck®. After informed consent, each patient participant is randomized to receive either two cervical dilation examinations with standard methods or two cervical dilation examinations using the device. Two practitioners complete the cervical examinations separately. The primary outcome is inter-examiner agreement between the control and device arms. Secondary outcomes include agreement of subjective measurements with DilaCheck® measurements over time, agreement of providers' device readings with a blinded reviewer's, patient and provider satisfaction, and documentation of adverse events. Planned enrollment is 50 participants over one year. We hypothesize that the device will increase agreement between the two practitioners from about 49% to 90%, as demonstrated in the simulator trial. The long-term objective is to validate DilaCheck® for use in increasing precision in cervical dilation measurements so that this tool may be available to Labor and Delivery providers to enhance quality of care for pregnant mothers. Increased precision in cervical dilation measurements will enable providers

to make better recommendations for admission to the hospital, augmentation or induction of labor, and cesarean section.

The proposed study is a randomized, controlled trial comparing inter-examiner agreement of standard methods for measuring cervical dilation to a novel medical device. The research population is pregnant women in the first stage of labor.

TRIAL PROTOCOL

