Photograph Review. The Sponsor will train an independent reviewer to read DilaCheck® measurements. The reviewer will be provided the photographs taken of DilaCheck® measurements. The reviewer will report two measurements for each photograph. The first will be his/her reading of the exact DilaCheck® measurement, which may be a fraction. The second reading will be his/her reading of the DilaCheck® measurement rounded to the nearest integer; i.e. the second response can only be an integer, not a fraction.

Continuous Feedback. After any individual provider completes five examinations with DilaCheck®, the provider will be provided feedback about whether his/her DilaCheck® measurement readings match those of the independent reviewer.

Power Calculation. The planned enrollment in the study is 50 patients. The following assumptions were used for the power calculations. The agreement in the Control Group was projected to be 49%,⁴ and the agreement in the Device Group was projected to be 90%, based on the results of the simulator trial. The standard deviation was projected to be 23, also based on the standard deviation in the prior simulator trial. With a two-tailed test with $\alpha=0.05$, a sample size of five yields 80% power. However, a trial with five participants will not yield the desired robustness in evaluation of a novel medical device. Instead, a sample size of 25 subjects in each group is planned to allow for examinations across a wide range of patients and providers. A sample size of 50 yields a power of 100% to detect a difference between the two methods given the above assumptions.

Statistical Analysis. The statistical analysis will use a two-tailed level of significance of 0.05. Using SPSS, the proportion of examinations in each group for which the two providers' examinations differed will be determined. A Students T test will be performed to determine whether this difference is significant. The number of examinations for which providers' answers differed by one centimeter and by two or more centimeters for each group will be determined. A Students T test will be performed to determine if the frequency of variation of one centimeter significantly differed between groups. A Students T test will be performed to determine if the frequency of variation of two or more centimeters significantly differed between groups. These analyses will be completed for both the fractional and integral (non-fractional) sets of DilaCheck® measurement readings.

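### The 90% device agreement behind the power statement is presented as a simulator result, but the simulator results reported are accuracy, so 90% in women is an assumption and the single 100% power figure hides how much depends on it.

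*Combined protocol and SAP*

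**What the plan says.** The Protocol Summary gives the hypothesis: "We hypothesize that the device will increase agreement between the two practitioners from about 49% to 90%, as demonstrated in the simulator trial". The Power Calculation section repeats the attribution: "the agreement in the Device Group was projected to be 90%, based on the results of the simulator trial". The same section takes the control figure from a published study ("The agreement in the Control Group was projected to be 49" percent, reference 4) and the spread from the simulator work: "The standard deviation was projected to be 23, also based on the standard deviation in the prior simulator trial". It concludes that a sample size of five gives 80% power and that the planned 50 patients give 100%.

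The simulator trial is described in the Protocol Summary. Fifty practitioners examined a simulator by standard methods and then with the device. The result is "Standard methods yielded an accuracy of 46%. With the device, accuracy increased to 96" percent, together with error rates of a stated size relative to the true value. The 49% comes from elsewhere in that section, where two practitioners examining laboring women are said to have had "measurements agree only 49% of the time".

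**The concern.** The trial's primary outcome is agreement between two examiners. Accuracy against a known opening is a different quantity. Two accurate readers usually agree, but two inaccurate readers can also agree, and two precise readers can round apart when the true dilation lies near a half-centimeter boundary. A simulator result stated as accuracy therefore does not demonstrate any particular level of agreement in women, and neither 49% nor 90% is among the simulator results reported.

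The 41-point difference (90 − 49) drives the power statement. A reader told that power is 100%, on the strength of a demonstrated effect, would take a non-significant result as evidence that the device failed. That reading is not justified if the true device agreement is well above 49% but short of 90%.

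**Working it through.** **Inputs.** From the Power Calculation and Statistical Analysis sections: control agreement 49%, device agreement 90%, SD 23 (read as percentage points), two-sided α = 0.05, 25 per arm. From the Protocol Summary: simulator accuracy 46% and 96%.

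**1. The plan's own figures.** Normal approximation for two means, difference 41, SD 23:

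- Power = Φ(41 / (23 × √(2/n)) − 1.96).
- n = 5 per group: 41 / (23 × √0.4) = 2.82, power 80.5%.
- n = 25 per group: 41 / (23 × √0.08) = 6.30, power 99.999%.

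Both stated figures reproduce if five means five per group. The arithmetic follows from its inputs; the question is the inputs.

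**2. What the simulator result can and cannot give.** Suppose each reader is independently correct 96% of the time on a fixed opening, and the 4% of errors are 1 cm, split evenly high and low:

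- Agreement = 0.96² + 2 × 0.02² = 0.9224, about 92%.
- If all errors fall on one side: 0.96² + 0.04² = 0.9232, also about 92%.

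So 90% is a reasonable figure for a simulator with fixed openings. Carrying it to women needs further facts that the protocol does not give: whether simulator openings were whole or fractional, what counted as an accurate reading, and how far two examiners' errors go together. Trying different answers while holding accuracy at 96% gives whole-centimeter agreement from about 50% to 94%. That range is a set of modeling scenarios, not an estimate.

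**3. Power across that uncertainty.** The primary outcome for each patient is yes or no. Power was found by enumerating all pairs of binomial counts with 25 per arm and control agreement 49%, applying each test at two-sided 0.05:

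| Device agreement | t test on 0/1 data (planned) | Fisher exact |
|---|---|---|
| 70% | 36% | 26% |
| 75% | 51% | 39% |
| 80% | 67% | 54% |
| 85% | 81% | 70% |
| 90% | 92% | 85% |
| 95% | 98% | 96% |

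**4. Separating two effects.** At 90% agreement the planned test has 92% power, not 100%. That drop is due only to the SD. For a yes/no outcome the SD is √(0.49 × 0.51) = 0.50 in the control arm and √(0.90 × 0.10) = 0.30 in the device arm, that is 50 and 30 points against the 23 assumed. The fall from 92% down the table is the part that depends on the unsupported 90%.

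**The case against.** Several points on the other side stand. The protocol says projected, hypothesized and given the stated assumptions, and its Human Subjects section concedes that the device's true value is unknown until it is tested in humans. The Power Calculation names a source for each arm, so it would be wrong to say that the effect has no source. The Protocol Summary is only a summary: the SD of 23 is attributed to the simulator trial without appearing there, so agreement data may exist in a report that we cannot see. The supportable statement is that agreement is not shown in these documents. The 25 per arm was also chosen for breadth of patients and providers, not to reach a power target.

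A reader might go further and infer that the simulator precision implies only about 73% agreement in women, with power of 43% (t test) or 32% (Fisher). The documents do not support that:

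- It requires whole-centimeter simulator openings, normal, unbiased and independent errors, evenly spread dilation, and an accurate reading meaning within half a centimeter. None of these is stated.
- The same model fitted to 46% accuracy predicts about 33% agreement for standard methods, below the 49% cited in laboring women, so it may understate agreement.
- The low power comes largely from applying the model to one arm only. With modeled figures in both arms (33% against 72.5%), power is 85% by t test and 77% by Fisher.

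Nor can one infer from 46% accuracy and 10.5% large errors that standard-method agreement is capped at about 41%. That treats every opening as having the same error distribution; if examiners misread particular openings in the same way, agreement can be higher. The plan in any case does not take its control figure from the simulator.

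What the objection does not remove is the word demonstrated, or the single power figure with no sensitivity to its main input.

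**Conclusion.** The concern holds as a matter of sourcing and presentation. The documents attribute a rise in agreement "from about 49% to 90%, as demonstrated in the simulator trial", but the results they report from that trial are accuracy only. The 90% should be read as a plausible assumption for women, neither demonstrated nor refuted.

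Its size is the spread in the table: over device agreement of 70% to 95%, power with the planned test runs from 36% to 98%, and from 26% to 96% with Fisher's test. Those figures assume control agreement of 49%, independent patients and 25 complete pairs per arm. The stated 100% does not hold for a yes/no outcome even at 90% agreement, but that part belongs to the SD of 23 and would remain if the 90% were fully sourced. The documents do not establish which row of the table is true, so they do not show that the trial is underpowered.

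**What to change.** In the Protocol Summary, remove the claim of demonstration. State that the simulator trial showed accuracy of 46% with standard methods and 96% with the device, and that 90% agreement in women is an assumption.

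In the Power Calculation, make the same change to the source of the 90%. Replace the 100% with power at 25 per arm against 49% for device agreement of 70, 75, 80, 85, 90 and 95%: 36, 51, 67, 81, 92 and 98% for the planned t test on 0/1 data, and 26, 39, 54, 70, 85 and 96% for Fisher's exact test. Add a sentence saying that the change from 100% to 92% at 90% agreement comes from using the variance of a yes/no outcome in place of SD 23. If the sponsor holds two-examiner agreement data from the simulator trial, report them there.

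Keep the sample size. The cost is a few lines of text and a six-row table, with no extra patients or procedures. The only downside is that the stated power becomes less favorable.

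### The power calculation uses an SD of 23, which a yes/no agreement outcome cannot have at 49% and 90%; 25 per group gives about 92% power, not 100%.

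*Combined protocol and SAP*

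**What the plan says.** The Power Calculation section projects 49% agreement in the Control Group and 90% in the Device Group, with a two-tailed level of 0.05. It then gives a spread: "The standard deviation was projected to be 23, also based on the standard deviation in the prior simulator trial". From these inputs it states that "a sample size of five yields 80% power", sets that size aside ("However, a trial with five participants will not yield the desired robustness"), plans 25 per group, and says: "A sample size of 50 yields a power of 100% to detect a difference between the two methods given the above assumptions".

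The outcome to be analysed is described elsewhere:
- **Protocol Summary:** "each patient participant is randomized to receive either two cervical dilation examinations with standard methods or two cervical dilation examinations using the device". Each patient therefore yields one pair of readings by one method.
- **Statistical Analysis:** "the proportion of examinations in each group for which the two providers' examinations differed will be determined", followed by "A Students T test will be performed to determine whether this difference is significant".
- **Statistical Analysis, covariate models:** the likelihood of agreement is modelled by logistic regression, which again treats agreement as binary.
- **Statistical Analysis, missing data:** a patient lacking either reading is left out of the primary analysis, and nothing is imputed.

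The source of the SD, the simulator trial, is described in the Protocol Summary: "Fifty Labor and Delivery practitioners completed examinations using standard methods and then the device".

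**The concern.** A mean and an SD can be chosen separately for a continuous measurement, but not for a yes/no result, where the proportion determines the SD. The plan fixes both proportions and then brings in an SD that fits neither. That SD comes from a study with a different unit (practitioners rather than patients) and a different design (each practitioner used both methods). The documents do not say what quantity the 23 describes.

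Two things are at stake. First, the protocol claims a power that the design lacks at its own rates, and a reader told 100% would take a null result as near-proof that the device does not help. Second, an SD of 23 makes power look insensitive to the device rate. That rate is the least secure input: it is taken from a simulator study whose reported result, in the Protocol Summary, is accuracy and not agreement between two examiners in labour.

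**Working it through.** **Inputs.** From Power Calculation: rates 0.49 and 0.90 (difference 41 points), SD 23 (no unit given; percentage points assumed), two-sided 0.05, 25 per group. From Statistical Analysis: Student's t-test on the proportion of pairs that differ. Testing disagreement or agreement is equivalent.

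**1. Reproduce the plan's figures (two means, SD 23).**
- Standardised difference: d = 41/23 = 1.783.
- Size for 80% power: n = 2(1.960 + 0.842)²/d² = 4.94, so 5 per group.
- Normal-approximation power, Φ(d√(n/2) − 1.960): 80.5% at 5 per group and 99.999% at 25 per group.

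Both stated figures reproduce, so SD 23 is what produced them. The five is a per-group number, although the text goes on to call it a trial of five participants. By the noncentral t distribution, five per group gives 69.5% even with SD 23.

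**2. The SD that the rates imply.**
- Control: √(0.49 × 0.51) = 0.500.
- Device: √(0.90 × 0.10) = 0.300.
- Root mean square: √((0.2499 + 0.0900)/2) = 0.412.
- Rate needed for SD 0.23: p(1 − p) = 0.0529, so p = 0.056 or 0.944. Neither assumed rate is close to the first, and the control rate is far from both.

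**3. Exact power on the binary outcome.** For n per group, take every pair of counts (a, b) with a from Binomial(n, 0.49) and b from Binomial(n, device rate). Apply the pooled t-test to the 0/1 data and sum the probabilities of the pairs that reject at 0.05. Fisher's exact test is shown for comparison; the plan does not name it.

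| Per group | Device rate | Planned t-test | Fisher | Plan states |
|---|---|---|---|---|
| 25 | 90% | 92.3% | 85.1% | 100% |
| 5 | 90% | 32.0% | 13.0% | 80% |
| 25 | 85% (assumed) | 81.1% | 70.3% | – |
| 25 | 80% (assumed) | 66.5% | 54.1% | – |
| 22 | 90% | 87.8% | 80.5% | – |
| 20 | 90% | 85.4% | 76.4% | – |
| 18 | 90% | 80.3% | 69.1% | – |
| 17 | 90% | 76.9% | 64.8% | – |

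Approximate formulas agree at 25 per group and 90%: noncentral t with SD 0.412 gives 93.1%, and the pooled two-proportion formula gives 90.8%.

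**4. What SD 23 hides.** With device agreement of 80%, the difference is 31 points. SD 23 at 25 per group would still show 99.7% power (noncentral t), against 66.5% for the binary outcome.

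**5. Room for exclusions.** At 49% and 90%, the planned test keeps 80% power down to 18 evaluable patients per group, a loss of 7 of 25. Fisher's test keeps it down to 22, a loss of 3 of 25.

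**The case against.** The strongest reply is that little follows from the error. At the plan's own rates power is still above 80% with either test. The 25 per group was chosen to cover a range of patients and providers and not from this calculation. No decision rule uses the power figure, and the 100% is stated as conditional on the assumptions. All of this is correct. It limits the remedy to a restatement, but it does not make the SD compatible with the rates given in the same paragraph.

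Some narrower objections also have weight:
- **Test size.** The t-test on 0/1 data at 25 per group rejects 6.5% of the time when both groups are at 49% (5.4% when both are at 70%). Part of the 92% therefore comes from exceeding the nominal level. This is a reason to call the figure approximate and to show Fisher's 85% beside it.
- **Method dependence.** For 80% power, the two-proportion formula gives 19 per group, or 24 with continuity correction, against 18 by enumeration of the t-test.
- **Reading type.** The comparison is to be run on both fractional and integer device readings, and the plan does not say which one the 90% describes.
- **Alternative rates.** Device agreement of 85% or 80% has no source in the documents. These values show sensitivity only.
- **Clustering.** Providers examine repeatedly, so independence is an assumption. The documents give no provider count or correlation, and the same providers may serve both groups, so the effect on power cannot be estimated here.

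**Conclusion.** The concern holds. An SD of 23 cannot belong to the primary outcome at the assumed rates, and the two stated powers depend on it. At 49% against 90%, two-sided 0.05 and independent patients, the planned t-test has about 92% power at 25 per group instead of 100%, and about 32% at five per group instead of 80%. Type II error at the plan's own rates is thus about 8%, not nil. The trial is not underpowered under its assumptions. The fault is an overstated justification and a hidden dependence on the device rate, and it should be fixed without changing the design.

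**What to change.** Replace the SD-based calculation with a two-proportion calculation and delete the statements about five patients and 100% power. Suggested text:

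> With 25 patients per group, agreement of 49% in the Control Group and 90% in the Device Group, a nominal two-sided level of 0.05 and patients treated as independent, the planned test on the yes/no agreement outcome has about 92% power (about 85% with Fisher's exact test). Power is about 81% if Device Group agreement is 85% and about 67% if it is 80%. At the assumed rates, about 18 evaluable patients per group give 80% power with the planned test.

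Add a phrase saying whether the 90% refers to the fractional or the integer device readings. Keep N = 50 and its existing rationale.

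The cost is one reworded paragraph and a less favourable power figure. No extra patients are needed, and neither the design nor the analysis changes.

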Trial Coordination. After training, the Sponsor or the trial coordinator will orient the provider to the study protocol and assign every provider a unique Provider Number. The trial coordinator will arrange with the hospital staff to conduct the trial at scheduled times during the study period. Administration of the trial requires two hospital providers who have been trained to use the device, the trial coordinator,

and a patient.

Patient Enrollment. Hospital providers will screen patients who have been admitted to the Labor and Delivery unit for eligibility. Posters advertising the trial will also be displayed on the Labor and Delivery unit. Once identified, hospital providers will ask eligible patients if they are interested in participating. If a patient indicates interest, the trial coordinator will complete an informed consent. The patient will sign the Patient Informed Consent Form.

Randomization. The trial coordinator will assign the participant a Subject Number from one to 50, in sequential order. (The first patient enrolled is assigned #1, the second enrolled is assigned #2, and so on.) The trial coordinator will then randomize the patient to either the Control Group or the Device Group using a randomization matrix generated by a computer randomization program.

Data Collection. The trial coordinator will inform two trained providers that the patient has agreed to participate in the trial. The trial coordinator will accompany one hospital provider to the patient's hospital room. The second provider will wait outside the room, in a place where s/he cannot hear the interaction in the room. The trial coordinator will re-affirm consent with the patient.

If the patient is randomized to the Control Group: The first provider will introduce him/herself and inform the patient that s/he is going to conduct a cervical examination. The trial coordinator will record the time of the first exam. The provider will complete a cervical examination following the standard techniques s/he uses on a regular basis, using sterile gloves. The provider will dispose of the gloves. The first provider will write his/her measurement of cervical dilation on the first Data Collection Form and fold the sheet of paper. Readings may be integers or fractional answers. The coordinator will take the folded sheet of paper and will not read the value. The first provider will then leave the hospital room. S/he will not speak to the second provider.

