The second provider will enter the hospital room. The second provider will introduce him/herself to the patient and explain that s/he is going to perform a cervical examination. The trial coordinator will record the time of the second exam. The second exam must be completed within 10 minutes of the first exam. The second provider will complete a cervical examination following standard techniques. The provider will write his/her measurement of cervical dilation on a second Data Collection Form, fold the form, and hand it to the trial coordinator. Readings may be integers or fractional answers. The second provider will leave the room.

If the patient is in the Device Group: The first provider will introduce him/herself and inform the patient that s/he is going to conduct a cervical examination and confirm that the patient is ready to proceed. The trial coordinator will record the time of the first exam. The first provider will complete a cervical examination with a DilaCheck® device and sterile gloves using the techniques taught during training.

During or after the examination, before looking at the DilaCheck® device or his/her hand, the provider will verbally report his/her subjective cervical dilation measurement to the trial coordinator. Readings may be integers or fractional answers. The trial coordinator will record this number. The first provider will then look at the DilaCheck® device and read the measurement from the DilaCheck® measuring tape.

The trial coordinator will take a photograph from a secure camera of the DilaCheck® measurement. The trial coordinator may choose to take multiple photographs to ensure a clear image is captured. The coordinator and provider will use a neutral background to ensure no private health information (such as an image of the patient participant or hospital room) is included in the photograph. A white sheet of paper with the subject number will be provided to serve as a blank, secure background for the photograph(s).

The first provider will record two readings of the DilaCheck® measurement. The provider will write his/her measurements on the first Data Collection Form, fold the form, and hand it to the trial coordinator. The first will be his or her reading of the exact DilaCheck® measurement, which may be a fraction (any fraction). The second reading will be his or her reading of the DilaCheck® measurement rounded to the nearest integer; i.e. the second response can only be an integer, not a fraction.

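### In the fractional run, agreement is scored as identical or not with no tolerance, so the result depends on how finely each arm records its readings

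*Combined protocol and SAP*

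**What the plan says.** The Protocol Summary states that "The primary outcome is inter-examiner agreement between the control and device arms". It does not define agreement.

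Statistical Analysis supplies the scoring: "the proportion of examinations in each group for which the two providers' examinations differed will be determined", followed by a Student t test at a two-sided 0.05 level. Differences of one cm and of two or more cm are then counted separately. The section adds: "These analyses will be completed for both the fractional and integral (non-fractional) sets of DilaCheck® measurement readings".

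Data Collection defines the readings. In the Device Group each provider records two values from the tape: "The first will be his or her reading of the exact DilaCheck® measurement, which may be a fraction (any fraction)"; for the other, "the second response can only be an integer, not a fraction". In the Control Group each provider records one value: "Readings may be integers or fractional answers".

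No section gives a tolerance, a reading increment, the tape graduation, or a rule for which of the two device sets decides the primary comparison.

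**The concern.** Taken literally, two device readings of 4.2 and 4.3 cm are a disagreement. Two control readings of 4 and 4 cm are an agreement, even if the fingers behind them judged 3.6 and 4.4 cm. For a given measurement error, finer recording lowers the chance of an exact match. A device arm told to record the exact value, set against a control arm free to give whole centimetres, can lose on this score while its examiners are closer together.

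At stake is one of the two planned runs of the primary comparison. It could give a significant result in the wrong direction, alongside a whole-cm run that favours the device, with no stated rule for choosing between them.

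**Working it through.** **The plan's own figure.** Power Calculation assumes 49% v 90%, SD 23, two-sided 0.05. By the normal approximation, n per group = 2 × (1.96 + 0.842)² × (23/41)² = 2 × 7.85 × 0.315 = 4.94. The stated five for 80% power is thus reproduced if it means five per group, and 25 per group gives over 99.99%. This does not bear on the present point, except that it supplies the 49% and does not say which reading set the 90% refers to.

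**Inputs.** From the documents: control agreement 49%, 25 per arm, two-sided 0.05, Student t test on a yes/no outcome, and 96% simulator accuracy with the device. Assumed: true dilation uniform from 1 to 9.5 cm; independent normal reading errors; whole-cm simulator targets; recording increments of 0.1 to 1 cm.

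**Error SDs.** Device: 96% of readings within 0.5 cm of a whole-cm target gives SD = 0.5 / z(0.98) = 0.5 / 2.054 = 0.243 cm. Fingers: the SD giving 49% identical whole-cm readings is about 0.495 cm.

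**Mean absolute difference between two examiners,** 2 × SD / √π: device 2 × 0.243 / 1.772 = 0.27 cm; fingers 2 × 0.495 / 1.772 = 0.56 cm. Rounding to nearest does not change these means when true dilation is spread evenly over the grid.

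**Chance of identical readings.** With recording increment r and unrounded difference D, the chance that both readings fall in the same cell is the mean of max(0, 1 − |D|/r). It depends only on r relative to the SD. By simulation:

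| Recorded to | Device identical (SD 0.243) | Fingers identical (SD 0.495) | Fingers within 0.5 cm |
|---|---|---|---|
| 1 cm | 73% | 49% | 49% |
| 0.5 cm | 50% | 27% | 70% |
| 0.25 cm | 28% | 14% | 62% |
| 0.1 cm | 12% | 6% | 57% |

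The exact-match score for the same fingers falls from 49% to 6% with no change in examiner error.

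**The planned t-test at 25 v 25.** As an example, take 12/25 control and 5/25 device pairs agreeing. Pooled variance = (0.48 × 0.52 + 0.20 × 0.80)/2 × 25/24 = 0.2133; SE = √(0.2133 × 2/25) = 0.131; t = 0.28/0.131 = 2.14 on 48 df; p = 0.037, device worse. Summing over all outcomes, the chance that the device is significantly worse is:

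| Device read to | Controls in whole cm (49%) | Controls in half cm (27%) |
|---|---|---|
| 0.5 cm | 3% | about 0% |
| 0.25 cm | 37% | 2% |
| 0.1 cm | 86% | 30% |

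**Other device SDs, controls at 49%.** Read to 0.1 cm: SD 0.05 cm gives 48.5% identical and 3.5% significantly worse; SD 0.10 cm gives 27.0% and 39%; SD 0.15 cm gives 18.5% and 66%. Read to 0.25 cm: SD 0.10 cm gives 56.6% and 0.8%; SD 0.30 cm gives 22.8% and 52%. Read to 0.5 cm: SD 0.10 cm gives 77.4% and about 0%.

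**Whole-cm run.** At SD 0.243 cm, 73% of device pairs are identical, and a significantly worse result against 49% has a chance of about 0.

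**The case against.** The strongest reply is that the large figures need two things the documents do not establish: fine reading of the tape, and control providers who record only whole centimetres. Control readings may be fractional. If the same fingers are recorded to half cm, control agreement is 27% and 37% and 86% fall to about 2% and 30%. If the device is read to 0.5 cm, nothing exceeds chance even against whole-cm controls; against half-cm controls the device is significantly better in about 40% of trials. The device SD is also inferred; it implies 73% whole-cm agreement, below the plan's 90%. All of this stands, and it is why the size is given as a range over both arms' increments.

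A reader might infer that the fractional run is biased against the device by construction. The documents do not support that: the direction depends on increments they leave open, and it can go either way.

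The whole-cm run and the one-cm and two-or-more-cm counts also give a reader some protection. They soften the consequence but do not cure the rule: neither sets a tolerance for the fractional run, the counts have no category below one cm, and the fractional run is not made subordinate.

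A reader might also infer that a fixed tolerance such as 0.5 cm settles the matter. It does not: the same fingers score from 49% to 70% within 0.5 cm, depending on the increment.

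**Conclusion.** The point holds as a dependence on recording increment. The fractional run scores identical or not, without a tolerance, on readings whose fineness is unspecified in both arms. At an assumed device SD of 0.24 cm with 25 per arm, the chance of a significant result against the device runs from about 0% (device and controls both to 0.5 cm) to 86% (device to 0.1 cm, controls in whole cm). Under every combination the device's mean examiner difference is about half that of fingers. The figures rest on the assumed SDs, normal errors and evenly spread dilation. The scoring problem itself rests only on the wording of the plan.

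The plan should be changed, but this does not show that the trial will reach a wrong conclusion: the whole-cm run does not show the reversal, and the fractional run shows it beyond chance only with finer device reading than control recording.

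**What to change.** In Statistical Analysis, for the fractional set, replace the identical-or-not comparison with a two-sample comparison of the absolute difference in cm between the two providers' recorded readings, computed identically in both arms. Keep exact equality for whole-cm readings only. The mean absolute difference stays near 0.56 cm for fingers and 0.27 cm for the device at every increment examined.

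If a proportion within a tolerance is also wanted, fix the tolerance before the data are seen and present it as supportive, because it still depends on the increment.

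The cost is a sentence or two of analysis wording, with no new data, patients or procedures. There are two downsides. The fractional result becomes a difference in cm, not a percent agreement. Power is moderate, about 56% to 79% under these assumptions; it varies because coarser recording widens the spread of the differences even where the mean is unchanged. The change does not settle which run decides the primary comparison; the plan still has to say so.
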